2.4.4 Safety Endpoints

Occurrence of adverse events will be evaluated, recorded, and followed up as required.

2.5 Acceptance Criteria

2.5.1 Primary Objective

BD Nano™ PRO non-inferior to Terumo Nanopass® for injection pain with partially blinded injections based on relative VAS, where -75mm indicates worse pain for BD Nano™ PRO and +75mm indicates worse pain for Terumo Nanopass® with a non-inferiority criterion of -10mm.

2.5.2 Secondary Objectives

- The BD Nano™ PRO will be evaluated for superiority vs Terumo Nanopass® for leakage, injection force, and bending.
- If the BD Nano™ PRO demonstrates non-inferiority for injection pain for the Primary Objective, compare the BD Nano™ PRO vs Terumo Nanopass® for superiority.

2.5.3 Exploratory Objectives

No formal acceptance criterion has been established for the following objectives - time to deliver dose, total injection time, and survey responses after all injections completed.

3 Sample Size

Leakage data is currently being used to calculate sample size.

Based on previous study data (BDT-2P00116) where leakage is equal to or greater than 1.5U was observed in 20/298 (6.7%) of injections performed with Terumo Nanopass® and in 3/297 (1%) of injections performed with BD Nano™ PRO, a simulation was performed (code found in SVN repository under DBC-18PENDL01Size Bayesian prior proportion.R) indicating that 292 injections per each pen needle type would provide 90% power to show BD Nano™ PRO superiority to Terumo Nanopass®. If each Subject tests 6 pairs of pen needles, 292 injections per each pen needle requires 49 subjects (rounded to 50 subjects). 50 Subjects will generate data for 600 pen needles: 300 pen needle pairs - 300 BD Nano™ PRO and 300 Terumo Nanopass®. A 10% buffer was added (to compensate for subject attrition or unusable data), leading to a planned enrollment number of 55 subjects.

Pain: Assuming the SD for relative VAS is around 50mm (based on DBC-17NUCLS07), a sample size of 300 pairs (50 Subjects x 6 pairs) has >90% power of passing a -10mm NI criteria, assuming a true average of -0.5mm in favor of Terumo Nanopass® (based on a 2-sided 95% CI for the mean).

4 Intended Statistical Software

This document was generated with R version 3.5.1 (2018-07-02) and the following packages (version) were used: assertthat (0.2.0), base (3.5.1), BD basics (0.2.4), bindr (0.1.1), bindrcpp (0.2.2), colorspace (1.3.2), compiler (3.5.1), crayon (1.3.4), datasets (3.5.1), dplyr (0.7.6), ggplot2 (3.0.0), glue (1.3.0), graphics (3.5.1), grDevices (3.5.1), grid (3.5.1), gtable (0.2.0), lattice (0.20.35), lazyeval (0.2.1), magrittr (1.5), methods (3.5.1), munsell (0.5.0), nlme (3.1.137), pillar (1.3.0), pkgconfig (2.0.2), plyr (1.8.4), purrr (0.2.5), R6 (2.2.2), Rcpp (0.12.18), reshape2 (1.4.3), rJava (0.9.10), rlang (0.2.2), scales (1.0.0), stats (3.5.1), stringi (1.1.7), stringr (1.3.1), tibble (1.4.2), tidyselect (0.2.4), tools (3.5.1), utils (3.5.1), withr (2.1.2), xlsx (0.6.1), xlsxjars (0.6.1), xtable (1.8.3).

The study will be conducted within the same environment or more recent versions.

5 Data

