### **7.3 Replacement of Discontinued Subjects/Specimens**

Recruitment of 60 Subjects is anticipated to accommodate potential subject attrition.

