### **13.1 Sample Size Determination**

Leakage data is currently being used to calculate sample size.

Based on previous study data (BDT-2P00116) where leakage  $\geq 1.5\text{U}$  was observed in 20/298 (6.7%) of injections performed with Terumo Nanopass® and in 3/297 (1%) of injections performed with BD Nano™ PRO, a simulation was performed (code found in SVN repository under DBC-18PENDL01\Stat\Sample Size\ Bayesian prior proportion R) indicating that 292 injections per each pen needle type would provide 90% power to show BD Nano™ PRO superiority to Terumo Nanopass®. If each Subject tests 6 pairs of pen needles, 292 injections per each pen needle requires 49 subjects (rounded to 50 subjects). 50 Subjects will generate data for 600 pen needles: 300 pen needle pairs; 300 BD Nano™ PRO and 300 Terumo Nanopass®. A 10% buffer was added (to compensate for subject attrition or unusable data), leading to a planned enrollment number of 55 subjects.

**Pain:** Assuming the SD for relative VAS is  $\sim 50\text{mm}$  (based on DBC-17NUCLS07), a sample size of 300 pairs (50 Subjects  $\times$  6 pairs) has  $>90\%$  power of passing a  $-10\text{mm}$  NI criteria, assuming a true average of  $-0.5\text{mm}$  in favor of Terumo Nanopass® (based on a 2-sided 95% CI for the mean).

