6.2.1 Analysis of Injection pain

A two-sided 95% confidence intervals will be calculated for the average rating. A modeling approach will be used to adjust for the pair order effect, BD order effect within pair (due to the often-observed bias towards favoring the last pen needle used in a pair), abdomen site effect and random subject effect. Results will be tested for non-inferiority, followed by superiority:

- If the lower bound of the CI is $> -10\text{mm}$, we can conclude in non-inferiority.
- If the lower bound of the CI is $> 0\text{mm}$, we can conclude in superiority.

```

> #####
> ## Example R code to fit a linear model
> #####
> ##
> ## fitting the model
> library(lme4)
> model.fit=lmer(vas_analysis ~ BD_NANO_ORDER + PAIR_ORDER + ABDOMEN_SITE
+                  +(1|SUBJ_ID),
+                  data=dataset, na.action=na.omit)
>

```

```

> ## Example for estimated pen needle subgroup means
> ##      if the lower CL is > -10, non-inferiority is satisfied
> ##      if the lower CL is > 0, superiority is satisfied
> library(emmeans)
> emmeans(model.fit, ~1)

```

```

1          emmean      SE      df lower.CL upper.CL
overall  24.10616 3.666296 145.14 16.85993 31.35238

```

Degrees-of-freedom method: kenward-roger
 Confidence level used: 0.95

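### The >90% power stated for the primary pain non-inferiority test is reproduced only by treating six scores per subject as independent, with almost no room for within-subject correlation

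*SAP*

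**What the plan says.** Enrolment was set on leakage. The only power statement for the primary objective is the pain paragraph in Protocol 13.1 and SAP section 3. The SAP says that "a sample size of 300 pairs (50 Subjects x 6 pairs) has >90% power of passing a -10mm NI criteria", and the Protocol has the same sentence ("a sample size of 300 pairs (50 Subjects" × 6 pairs). The inputs are a true mean of -0.5 mm, a decision rule "based on a 2-sided 95% CI for the mean", and an SD introduced as follows: "Assuming the SD for relative VAS is around 50mm (based on DBC-17NUCLS07"). The margin is set in SAP 2.5.1 "with a non-inferiority criterion of -10mm".

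Each subject gives one relative VAS score per pair, hence six scores. SAP 6.2.1 analyses them with a mixed model that adjusts for pair order, BD order within pair, "abdomen site effect and random subject effect. Results will be tested for non-inferiority, followed by superiority". The example code includes `(1|SUBJ_ID)`.

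Planned enrolment is 55, which includes a 10% buffer. Protocol 7.3 adds: "Recruitment of 60 Subjects is anticipated to accommodate potential subject attrition".

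**The concern.** The power sentence counts pairs, whereas the analysis model recognises that pairs are grouped within subjects. Pairing does not remove this grouping. Each score is already a BD-versus-Terumo comparison, so what remains between subjects is each person's own tendency to favour one needle. Such a tendency is plausible here: Protocol 3.4.2 accepts that subjects will know which needle type they are using, and they judge the same two needles six times in one visit.

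If scores from one subject are positively correlated, 300 pairs carry less information than 300 independent observations, and the chance of missing a true non-inferiority result is higher than stated. A missed primary result would then be read against a claimed power above 90%. It would also block the pain superiority evaluation, which is conditional on non-inferiority.

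**Working it through.** **Inputs from the documents.** Margin -10 mm; true mean -0.5 mm, so the distance to the margin is 9.5 mm; two-sided 95% CI (z = 1.960); SD 50 mm; 6 pairs per subject; 50 subjects for power, 55 planned, 60 anticipated. The ICC is not given, so it is an assumption and is varied below.

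**Step 1: reproduce the stated figure.** With 300 independent pairs, SE = 50/√300 = 2.89 mm, and power = Φ(9.5/2.89 − 1.960) = 90.8%. This matches the stated >90%, with 0.8 points to spare. The number of independent pairs needed for 90% is (50 × (1.960 + 1.2816)/9.5)² = 291.1, against 300 available. The pain power method is not described, so independence is inferred from this match.

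**Step 2: allow for six scores per subject.** With N subjects,

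SE = SD × √((1 + 5·ICC)/(6N)), and power = Φ(9.5/SE − 1.960).

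Example, N = 50 and ICC = 0.10: effective n = 300/1.5 = 200, SE = 50/√200 = 3.54 mm, power 76.6%.

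| ICC (assumed) | 50 subjects | 55 subjects | 60 subjects |
|---|---|---|---|
| 0 | 90.8% | 93.2% | 95.0% |
| 0.05 | 83.7% | 87.0% | 89.7% |
| 0.10 | 76.6% | 80.5% | 83.7% |
| 0.20 | 64.3% | 68.5% | 72.2% |

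The columns for 55 and 60 assume that every subject supplies all six pairs, so they are upper bounds: those numbers exist to absorb attrition.

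**Step 3: the ICC at which power falls to 90%.** Solving 6N/(1 + 5·ICC) = 291.1 gives ICC = (6N/291.1 − 1)/5 = 0.006, 0.027 and 0.047 for N = 50, 55 and 60. Expressed as a between-subject SD of true preference, 50 × √ICC, these are about 4, 8 and 11 mm on a 150 mm scale.

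**Step 4: small-sample check.** A noncentral t calculation on subject means (N − 1 df) is 1 to 2 points lower. With 50 subjects it gives 89.7% at ICC 0, already just under 90%, then 82.3%, 75.0% and 62.6% at ICC 0.05, 0.10 and 0.20. A random-intercept simulation (40,000 trials per setting) gave 75.5%, 79.0% and 82.5% for 50, 55 and 60 subjects at ICC 0.10.

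**Step 5: sensitivity to the other inputs (normal approximation).**

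| Change | 90% threshold: 50 / 55 / 60 subjects | Power at ICC 0.10: 50 / 55 / 60 |
|---|---|---|
| As planned (SD 50, mean -0.5) | 0.006 / 0.027 / 0.047 | 76.6 / 80.5 / 83.7% |
| True mean 0 mm | 0.028 / 0.051 / 0.074 | 80.7 / 84.3 / 87.3% |
| Assumed ±20 mm order effect removed: SD √(2500 − 400) = 45.8 | 0.045 / 0.070 / 0.095 | 83.4 / 86.8 / 89.5% |
| SD 45 mm | 0.054 / 0.080 / 0.105 | 84.7 / 87.9 / 90.5% |
| SD 43.3 mm (uniform over the scale, 150/√12) | 0.075 / 0.102 / 0.130 | 87.3 / 90.2 / 92.5% |

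In the other direction, if 50 mm is the within-subject SD, the total SD is 50/√(1 − ICC), and power with 50 subjects is 81.8%, 72.2% and 54.8% at ICC 0.05, 0.10 and 0.20.

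**The case against.** The strongest reply is that no shortfall has been shown. The ICC, the meaning of the 50 mm and the sponsor's method are all unstated, and the figures that would settle them lie in a study not available here. That stands: the documents support saying that the power figure omits its clustering assumption, not that power is below 90% by a known amount.

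The 0.006 threshold should also not be read as precise. The SD is only approximate: at 49.5 mm the 50-subject threshold is 0.010 and at 49 mm it is 0.015, while on the t calculation there is no threshold at all because power is already 89.7% at ICC 0. The useful reading is that the margin for correlation is close to nil at 50 subjects.

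Some assumptions may be cautious. A uniform spread over the bounded scale has SD 43.3 mm, so 50 mm is large for a total SD, although relative scores can be bimodal. The same bound makes the within-subject reading less comfortable, since it needs a total SD of 55.9 mm at ICC 0.20. The SAP also expects an order effect ("due to the often-observed bias towards favoring the last pen needle used in a pair"), and its removal should reduce variance if the 50 mm includes it. Enrolment of 55 or 60 with few dropouts would help as well. Step 5 shows that these move the threshold up, in places past 0.10, but none secures 90% without knowledge of the ICC.

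Finally, enrolment was set on leakage, and low power is the sponsor's own risk: it does not weaken a positive result. That is a fair argument about weight. Against it, this is the only power statement the primary objective has.

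**Conclusion.** The concern holds. The >90% figure is reproduced by a calculation on 300 independent pairs, and it leaves almost no room for the within-subject correlation that the SAP model itself provides for. With 50 mm as total SD and no covariate gain, an ICC of 0.10 would give 76.6% with 50 subjects, 80.5% with 55 and at most 83.7% with 60. The size of any loss depends on an ICC that the documents do not give, on whether 50 mm is a total or within-subject SD, and on how much variance the order and site terms remove.

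This is a matter of power. Under the SAP model the subject effect is included, so type I error is not at stake. A check using a subject-mean t interval at a true mean of -10 mm gave 2.50%, 2.47% and 2.43% at ICC 0, 0.10 and 0.20; it did not run the planned `lmer` model itself. The reassurance depends on the SAP's firm commitment to the model, because Protocol 13.3 says only that modelling may be used. The point should be fixed, but it does not threaten the validity of a positive result.

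**What to change.** In Protocol 13.1 and SAP section 3:

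1. State whether 50 mm is the total or the within-subject SD, and whether it includes the within-pair order effect that the model removes.
2. Give the ICC, or the between- and within-subject variances, from DBC-17NUCLS07.
3. Recompute power for the planned mixed model, with effective n = 300/(1 + 5·ICC) as a first approximation, and replace >90% with the result. If no ICC estimate can be obtained, give a range over ICC instead.

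The cost is one or two sentences in each document and a variance-component estimate from a study the sponsor already cites. The stated power may become less favourable. No change to enrolment, analysis or decision rule is needed for this point.

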5.1 Database Information

The input data will consist in several csv (comma separated values) files exported from Clindex.

Files will be saved in

https://svn.bdx.com:8443/svn/stats_and_dm/DM_and_Stats_Outputs/DBC/DBC-18PENDL01/Data
and read directly into R for analysis.

5.2 Analysis Population Set(s)

All data collected will be analyzed and reviewed for possible exclusion based on significant outliers or protocol deviations.

Injections where bleeding was observed will not be used in the leakage analyses.

Analyses of relative data will only include pairs where both injections were completed.

Demographic information and Diabetes history collected for all subjects randomized will be tabulated.

Data from all subjects will be included in the summary of safety parameters.

6 Statistical Analysis / Calculations

6.1 Derived Variables

6.1.1 Relative VAS Scale

After completion of each pair of injection, subjects will be asked to compare pain between the pen needles using a 150mm relative VAS Scale. Marks made on the 150mm relative VAS Scale are read using a 0 - 20 grid and the resulting discrete scores entered into the database. The results will be transformed to a [-75mm, 75mm] scale for analysis and reporting, where positive scores will reflect less pain for BD Nano Pro and negative scores will reflect less pain for Terumo.

Subjects will draw a vertical line on a relative VAS scale for each pair of injections, to indicate their relative pain perception for the pen needle used first or second in the pair. A vertical line drawn to the left of the center mark indicates that the 1st injection was less painful. A vertical line drawn to the right of the center mark indicates that the 2nd injection was less painful. A vertical line drawn at the center mark indicates no difference. Figure 1 shows an example of a 150mm (may not be to scale) relative VAS scale.

The scores are entered into the database on a discrete 0 – 20 scale. These scores will be transformed to a 150mm VAS on a [-75mm, 75mm] scale as follows:

Let $Y_{recorded}$ ($= 0, 1, \dots, 20$) be the recorded VAS score, the first transformation for the analysis of VAS score, $Y_{analysis}^*$ (mm), will be calculated as:

$$Y_{analysis}^* = \frac{150}{20} * Y_{recorded} - 75 \quad (1)$$

The sign of the VAS responses $Y_{analysis}^*$ will then be adjusted depending on which pen needle was used in the first and in the second injection, so that positive scores (+) will reflect less pain for BD Nano and negative scores (-) will reflect less pain for Terumo. Let $Y_{analysis}$ be the final relative VAS score used for the analysis. Then:

$$Y_{analysis} = \begin{cases} Y_{analysis}^*, & \text{if BD Nano is provided in the 2nd injection} \\ -Y_{analysis}^*, & \text{if BD Nano is provided in the 1st injection} \end{cases} \quad (2)$$

Which injection was less painful?

[figure not shown]

Figure 1: VAS Scale for Injection Pain

6.1.2 Leakage Scale

Study Staff will use the provided materials and scale to absorb leakage from the pen needle tip and injection site to measure the amount of leakage. Leakage will be considered to be present if measurement is equivalent to or greater than 5% of dose (equivalent to equal to or greater than 1.5U of U100 insulin (or 0.015g)). A binary leakage variable will be created with the equation below:

$$Y_{Leakage} = \begin{cases} \text{Yes, if recorded leakage} \geq 0.015g \\ \text{No, if recorded leakage} < 0.015g \end{cases} \quad (3)$$

6.1.3 Injection force

Injection force will be evaluated after each pair of injections using a 5-point Likert scale and the results will be converted to ratings of -2 to 2 as below:

$$Y_{Injectionforce}^* = \begin{cases} -2, & \text{if 1st injection significantly less thumb force} \\ -1, & \text{if 1st injection slightly less thumb force} \\ 0, & \text{if no difference} \\ 1, & \text{if 2nd injection slightly less thumb force} \\ 2, & \text{if 2nd injection significantly less thumb force} \end{cases} \quad (4)$$

The sign of the injection force responses $Y_{Injectionforce}^*$ will then be adjusted depending on which pen needle was used in the first and in the second injection, so that positive scores (+) will reflect less thumb force for BD Nano and negative scores (-) will reflect less thumb force for Terumo. Let $Y_{Injectionforce}$ be the final injection force score used for the analysis. Then:

$$Y_{Injectionforce} = \begin{cases} Y_{Injectionforce}^*, & \text{if BD Nano is provided in the 2nd injection} \\ -Y_{Injectionforce}^*, & \text{if BD Nano is provided in the 1st injection} \end{cases} \quad (5)$$

The responses will also be converted to 3 categories: favoring Terumo Nanopass[®] (negative ratings), no difference (0 ratings) and favoring BD Nano[™] PRO (positive ratings) with the equation below:

$$Y_{Injectionforce(categorical)} = \begin{cases} \text{Terumo with less injection force if recorded rating} < 0 \\ \text{No difference, if recorded rating} = 0 \\ \text{BD Nano with less injection force if recorded rating} > 0 \end{cases} \quad (6)$$

6.2 Analysis Method

This section provides a detailed description of the statistical analysis that will be performed in this study.

Unless otherwise stated, all the statistical tests are two-sided at a significance level of 5%.

Summary statistics (number of observations, mean, 95% CI for mean, median, standard deviation and range) for all quantitative responses will be presented in tables. Frequency tables with number of observations, percentage of total will be created for all discrete responses.

Bar plots may be provided for some responses.

6.2.1 Analysis of Injection pain

A two-sided 95% confidence intervals will be calculated for the average rating. A modeling approach will be used to adjust for the pair order effect, BD order effect within pair (due to the often-observed bias towards favoring the last pen needle used in a pair), abdomen site effect and random subject effect. Results will be tested for non-inferiority, followed by superiority:

- If the lower bound of the CI is $> -10\text{mm}$, we can conclude in non-inferiority.
- If the lower bound of the CI is $> 0\text{mm}$, we can conclude in superiority.

```

> #####
> ## Example R code to fit a linear model
> #####
> ##
> ## fitting the model
> library(lme4)
> model.fit=lmer(vas_analysis ~ BD_NANO_ORDER + PAIR_ORDER + ABDOMEN_SITE
+                  +(1|SUBJ_ID),
+                  data=dataset, na.action=na.omit)
>

```

```

> ## Example for estimated pen needle subgroup means
> ##      if the lower CL is > -10, non-inferiority is satisfied
> ##      if the lower CL is > 0, superiority is satisfied
> library(emmeans)
> emmeans(model.fit, ~1)

```

```

1          emmean      SE      df lower.CL upper.CL
overall  24.10616 3.666296 145.14 16.85993 31.35238

```

Degrees-of-freedom method: kenward-roger
 Confidence level used: 0.95

6.2.2 Analysis of Injection force

The responses in 5-point Likert scale will be converted to ratings of -2 to 2 (where positive ratings favor BD, see section 6.1.3) and a two-sided 95% confidence interval will be calculated for the average rating. If the lower bound of the CI is > 0, we can conclude in superiority. A modeling approach will be used to adjust for the pair order effect, BD order effect within pair, abdomen site effect and random subject effect.

Responses will also be converted to 3 categories: favoring Terumo Nanopass[®] (negative ratings), no difference (0 ratings) and favoring BD Nano[™]PRO (positive ratings) (see Section 6.1.3). The difference in percentage of responses with a preference for BD Nano vs Terumo Nanopass will be calculated by Bayesian approach, adjusting for the “no preference” category.

6.2.3 Needle Bending and Leakage

Analysis will be performed using a binary logistic regression with random subject effect and fixed pen needle type effect, pair order effect, PN order effect within pair and abdomen site effect. The average difference in percentage of occurrence with BD PN and Terumo PN will be calculated with 95% confidence interval and assessed for statistical significance. The upper bound of the confidence interval will be compared to 0: superiority will be concluded given that the upper bound of the 95% confidence interval for the difference in proportions is < 0%.

```

> #####
> ## Example R code to fit a logistic regression model
> #####
> ##
> ## fitting the model
> library(lme4)
> library(lsmeans)
> model.fit=glmer(leakage ~ PN +BD_NANO_ORDER+ PAIR_ORDER + ABDOMEN_SITE
+                   +(1|SUBJ_ID),
+                   data=dataset, na.action=na.omit, family="binomial",
+                   control = glmerControl(optimizer = "bobyqa"),nAGQ = 10)
> lsm.out<-lsmeans(model.fit, ~PN, type="response")
> confint(pairs(regrid(lsm.out)))

```

```

contrast           estimate      SE df asymp.LCL asymp.UCL
BD Nano - Terumo -0.00000001142909 2759378 NA  -5408282   5408282

```

Confidence level used: 0.95

6.2.4 Analysis of Exploratory Objectives (Delivery time, Total injection time, Needle Breaking, and Non-Comparative Questionnaire)

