8.1.3 Executive Summary

A high level summary will be provided for each objective/endpoint (example below).

Primary Objective (examples only):

- *Injection Pain:* The lower bound of the CI for the average relative pain comparison between BD Nano™ PRO and Terumo Nanopass® met both non-inferiority and superiority criteria.

Secondary Objectives (examples only):

- *Injection force:* The lower bound of the CI for the average difference in rating of BD Nano™ PRO and Terumo Nanopass® injection force met the superiority criterion.
- *Needle Bending:* The upper bound of the CI for the average difference in percentage of needle bending occurrence with BD Nano™ PRO and Terumo Nanopass® met the superiority criterion.
- *Leakage:* The upper bound of the CI for the average difference in percentage of leakage occurrence with BD Nano™ PRO and Terumo Nanopass® met the superiority criterion.

In addition, a summary table for all primary and secondary objectives will be presented as in Table 2 (Example only). A blue check mark (✓) indicates that the acceptance criterion is met, while a red X mark (✗) indicates that the acceptance criterion is not met.

Table 2: Results Summary of primary and secondary objectives (Example only)

Objective	
Primary Objective	
Injection Pain (Non-inferiority)	✗
Injection Pain (Superiority)	✗
Secondary Objective	
Injection force	✓
Needle Bending	✓
Leakage	✓

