8.2.3 Needle Bending

Summary statistics for needle bending will be presented as in Table 9.

The results of difference in percentage of needle bending will be evaluated as presented in Table 10.

Table 9: Observed percentage of Needle Bending (Example only)

Pen Needle	Needle bending	95% CI
BD Nano	4/330 (1.2%)	[0.1%, 2%]
Terumo Nanopass	4/330 (1.2%)	[0.1%, 2%]

Table 10: Difference in Percentage of Needle Bending (Example only)

Comparison	Difference in Percentage of Needle bending based on modeling analysis.	95% CI for Difference
BD Nano vs Terumo Nanopass	-1.2%	[-2%, 0.8%]

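### The only interval construction SAP 6.2.3 gives for leakage and bending does not estimate the average difference being tested, and it breaks down when a site or factor-coded pair-order level has no event

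*SAP*

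**What the plan says.** Protocol 13.3 and SAP 6.2.3 specify a logistic model with a random subject effect and fixed effects for needle, pair order, order within pair and abdomen site. The tested quantity is worded as: "The average difference in percentage of occurrence with BD PN and Terumo PN will be calculated with 95% confidence interval". Superiority needs an upper bound below 0%. SAP 8.1.3 repeats the quantity ("The upper bound of the CI for the average difference in percentage of leakage occurrence"), and SAP Table 10 is headed "Difference in Percentage of Needle bending based on modeling analysis".

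Protocol 13.3 gives no construction for the interval. SAP 6.2.3 gives one, in a block headed as example code: the fit "model.fit=glmer(leakage ~ PN +BD_NANO_ORDER+ PAIR_ORDER + ABDOMEN_SITE", then "lsm.out<-lsmeans(model.fit, ~PN", then "confint(pairs(regrid(lsm.out". The printed illustration is "BD Nano - Terumo -0.00000001142909 2759378 NA", with limits of about ±5.4 million. Neither document says what to do if the fit does not converge or the interval cannot be estimated.

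SAP 3 sizes the trial on leakage: 20/298 against 3/297 in a previous study, 292 injections per needle, 90% power.

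**The concern.** The model is reasonable; the difficulty lies in the step from model to interval. Least-squares means average the linear predictor over factor levels with the random effect set to 0, and only then is the result turned into a probability. The inverse logit of an average is not the average of the probabilities, so the code and the sentence above it describe different quantities.

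The same averaging is fragile. A factor level with no event has no finite logit, and the average carries that level into both needles' means. With about 23 leakage events expected in 600 injections, an empty level is a realistic outcome.

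At stake is a secondary endpoint, but the one that set the sample size. A real leakage difference could go undeclared for a numerical reason, or be reported as smaller than it is. Bending follows the same rule; no bending rate is given, so no bending power can be checked.

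**Working it through.** **Inputs.** From SAP 3: Terumo 20/298 = 6.71%, BD 3/297 = 1.01%, difference −5.70 points; 50 subjects × 6 pairs = 300 injections per needle; 55 planned. From SAP 6.2.3: model, code and rule. Not in the text, so varied: number of abdomen sites (2 to 6), coding of pair order (numeric or six-level factor), and between-subject SD on the logit scale (0, 0.5, 1.0).

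**The stated 90%.** For two independent proportions at fixed rates, 90% power needs 238 per needle, and 292 gives 94.9%. If the rates are instead drawn from Beta posteriors based on 20/298 and 3/297 (my assumption, prompted by the simulation file's name), 292 gives 88–91%. So the figure reproduces as an average over uncertain rates, with no subject, order or site terms.

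**Quantity estimated.** Setting the random effect to 0 while holding the marginal rates at 6.71% and 1.01%:

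- SD 0.5: 0.90% − 6.07% = −5.2 points
- SD 1.0: 0.63% − 4.58% = −4.0 points

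Averaging estimated site and order effects on the logit scale shrinks the estimate further, because the inverse logit is convex at low rates. In simulated trials without an empty level (50 subjects), the mean coded estimate was −4.5 to −5.1 (SD 0), −4.3 to −4.8 (SD 0.5) and −3.3 to −3.9 (SD 1.0). A standardised difference from the same fits gave −5.6 to −5.8 throughout.

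**Chance of an empty level.** Each of six pair orders holds 50 injections per needle. P(no event in one level) = (1 − 0.0671)^50 × (1 − 0.0101)^50 = 0.0187. P(at least one empty) = 1 − (1 − 0.0187)^6 = 10.7%.

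**Effect of an empty level.** Let its logit run to −M in a factor with k levels. The averaged predictor moves by −M/k, so each probability shrinks like exp(−M/k). The coefficient's standard error grows like exp(M/2). The delta-method standard error therefore behaves like exp{M(1/2 − 1/k)}, which is unbounded for k > 2, while the estimate goes to 0.

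**Power of the coded step.** Random-intercept logistic model by maximum likelihood in Python (not lme4), 1000 trials per cell, no true order or site effect. Entries are percentages; n is subjects.

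| Pair order, sites | Empty level (n=50, SD 0) | n=50, SD 0 | n=50, SD 0.5 | n=50, SD 1.0 | n=55, SD 0 | n=55, SD 1.0 |
|---|---|---|---|---|---|---|
| numeric, 2 | 0 | 94 | 93 | 77 | 96 | 83 |
| numeric, 3 | 0.1 | 94 | 93 | 76 | 97 | 81 |
| numeric, 4 | 1.7 | 91 | 89 | 72 | 95 | 81 |
| numeric, 6 | 9.5 | 85 | 82 | 68 | 91 | 75 |
| factor, 2 | 12 | 82 | 80 | 66 | 88 | 74 |
| factor, 4 | 11 | 80 | 80 | 60 | 90 | 71 |
| factor, 6 | 19 | 74 | 72 | 55 | 82 | 67 |

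Separately coded runs agree in pattern but differ by up to about 6 points in a cell (numeric, six sites, SD 0: 79, 84 and 85%), so the entries should be read as rounded.

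The standardised difference from the same model, with a subject-robust interval, gave 96–98% at 50 subjects and 97–99% at 55 in every setting. In the 2691 simulated trials with an empty level, the coded step passed in 0 and the standardised difference in 2525.

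**Error rate of the replacement.** Over 16 null settings, its one-sided error was 1.7–2.9%, apart from one cell at 3.4% that gave 2.7% when rerun with 8000 trials.

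**Very few events.** Suppose four of 50 subjects have one Terumo event each and BD has none. The mean paired difference is −4/300 = −1.33 points, its SD 4.57, its SE 0.646, and the upper bound −1.333 + 2.010 × 0.646 = −0.04. A t interval would declare superiority, while the exact sign test gives p = 2 × 0.5^4 = 0.125. With five informative subjects the smallest possible p is 0.0625; with six it is 0.031.

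**The case against.** **It is only example code.** The block is labelled as an example, and the text above it names a suitable quantity, so a statistician who computed a standardised difference would comply. That is true, but no other construction or fallback is documented, so any substitute would be chosen after the data are seen. Protocol 13.0 allows justified deviations; it does not make them pre-specified.

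**Adjusted means are a legitimate reading of a model-based difference.** This has some force: the documents do not say marginal or conditional. But an average difference in percentage of occurrence is most naturally an average of percentages, and this reading does not cure the empty-level failure. The observed percentages in SAP Table 9, which leakage follows, soften the reporting concern but do not enter the decision.

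**The power loss rests on unknown inputs.** This stands. The code has no factor conversion and the files are "read directly into R for analysis", so pair order stored as 1 to 6 would be numeric and the factor rows would not apply. The number of sites may be in a figure that was not available. Protocol 7.3 anticipates recruiting 60. At 60 subjects with numeric pair order, four sites give 95% (SD 0), 95% (SD 0.5) and 83% (SD 1.0), and six sites give 93% (SD 0) and 90% (SD 0.5). Factor coding with six sites and SD 0 gives 88%.

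**Stronger readings.** A reader might infer from the printed standard error of 2,759,378 that the trial's own interval will collapse. It shows that the code can return an unusable interval, not how often; SAP 8 says its example tables come from database-test data and are not representative. A reader might also think that no BD event at all would block the rule. It does not by itself: 1345 of 1599 such simulated trials passed.

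**Conclusion.** The point holds. The construction in SAP 6.2.3 targets a smaller quantity than the one named (to the nearest half point, −3.5 to −5 against −5.7). It cannot declare superiority when a site (of more than two) or a factor-coded pair-order level is empty, and no fallback is stated.

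The error is conservative. It costs power on secondary endpoints, creates no false superiority claim, and leaves the primary pain analysis untouched.

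The documents do not support saying that the trial is underpowered for leakage or that the 90% is wrong. About 90% or more survives with numeric pair order, up to four sites and a subject SD of 0 to 0.5. At 50 subjects it falls to roughly 55–85% with factor-coded pair order, six sites or an SD of 1.0; at 55–60 it is higher, though at SD 1.0 no setting examined reached 90%. Nor do the documents show which method the cited power simulation used. The supported statement is that the 90% is not assured for the rule as coded.

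**What to change.** In SAP 6.2.3:

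- Keep the logistic mixed model. Replace the least-squares-means and back-transformation step with a standardised risk difference: predict each observed injection's probability under BD and under Terumo, average over injections and over the fitted subject random effect, and give a 95% interval clustered by subject (sandwich or bootstrap). Superiority if the upper bound is below 0.
- State how pair order is coded, and how many abdomen sites enter the model.
- Pre-specify the fallback for non-convergence or a non-estimable interval: the subject-level paired risk difference with a t-based 95% interval.
- When fewer than six subjects have an event, under either method, let the exact subject-level sign test govern, so that superiority is not declared on the interval alone.

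In SAP 3, restate the leakage power for the rule actually used, with its assumptions. Protocol 13.3 already names the right quantity and can stand.

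The cost is a few lines of code and some wording; conduct, sample size and adjustment are unchanged. The downside is that no superiority claim is possible with very few events, since five or fewer informative subjects cannot reach p < 0.05. At the planned leakage rates this hardly matters: about 16 to 19 of 50 subjects would be expected to have an event (SD 1.0 and SD 0). It could matter for bending, whose rate is unknown.
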